4.4 Study Subjects

This prospective RCT will enroll up to 240 subjects in up to 12 centers located in the USA.

4.4.1 Inclusion Criteria

Potential patients are required to meet all of the following criteria for enrollment into the study and subsequent randomization:

- 1. Subjects must be at least 18 years of age or older.
- 2. Subjects must have a diagnosis of type 1 or 2 Diabetes mellitus.
- 3. At randomization subjects must have a target diabetic foot ulcer with a minimum surface area of 1.0 cm² and a maximum surface area of 20.0 cm² measured post debridement with a photographic planimetry app.
- 4. The target ulcer must have been present for a minimum of 4 weeks and a maximum of 52 weeks of standard of care prior to the initial screening visit.
- 5. The target ulcer must be located on the foot with at least 50% of the ulcer below the malleolus.
- 6. The target ulcer must be full thickness on the foot or ankle that does not probe to bone
- 7. Adequate circulation to the affected foot as documented by any of the following methods performed within 3 months of the first screening visit:
 - a. TCOM ≥30 mmHg
 - b. ABI between 0.7 and 1.3
 - c. PVR: Biphasic
 - d. TBI >0.6
 - e. As an alternative arterial Doppler ultrasound can be performed evaluating for biphasic dorsalis pedis and posterior tibial vessels at the level of the ankle.
- 8. If the subject has two or more ulcers, they must be separated by at least 2 cm. The largest ulcer satisfying the inclusion and exclusion criteria will be designated as the target ulcer.
- 9. Target ulcers located on the plantar aspect of the foot must be offloaded for at least 14 days prior to randomization.
- 10. The subject must consent to using the prescribed off-loading method for the duration of the study.
- 11. The subject must agree to attend the weekly study visits required by the protocol.
- 12. The subject must be willing and able to participate in the informed consent process.

Patients must have read and signed the IRB approved ICF before screening procedures are undertaken.

4.4.2 Exclusion Criteria

Potential subjects meeting any of the following criteria will be excluded from enrollment and subsequent randomization:

Confidential Page 20 of 73

- 1. A subject known to have a life expectancy of < 6 months is excluded.
- 2. If the target ulcer is infected or if there is cellulitis in the surrounding skin, the subject is excluded.
- 3. Presence of osteomyelitis or exposed bone, probes to bone or joint capsule on investigator's exam or radiographic evidence.
- 4. A potential subject cannot have an infection in the target ulcer or in a remote location that requires systemic antibiotic therapy.
- A subject receiving immunosuppressants (including systemic corticosteroids at doses greater than 10 mg of Prednisone per day or equivalent) or cytotoxic chemotherapy is excluded.
- 6. The topical application of steroids to the ulcer surface within one month of initial screening is not permitted.
- 7. A subject with a previous partial amputation on the affected foot is excluded if the resulting deformity impedes proper offloading of the target ulcer.
- 8. If a subject has a glycated hemoglobin (HbA1c) greater than or equal to 12% taken at or within 3 months of the initial screening visit he/she is excluded.
- 9. If a subject has a serum creatinine ≥ 3.0mg/dL within 6 months of randomization he/she is excluded.
- 10. The subject is excluded if the surface area measurement of the target ulcer has reduced in size by more than 30% in the 2 weeks prior to the initial screening during the 2-week screening phase: the 2 weeks from the initial screening visit (SV1) to the TV1/randomization visit during which time the subject received SOC.
- 11. A Subject with an acute Charcot foot, or an inactive Charcot foot, that impedes proper offloading of the target ulcer is excluded.
- 12. Women who are pregnant or considering becoming pregnant within the next 6 months are excluded.
- 13. A potential subject with end stage renal disease requiring dialysis is excluded.
- 14. A subject who participated in a clinical trial involving treatment with an investigational product within the previous 30 days is excluded.
- 15. A subject who, in the opinion of the Investigator, has a medical or psychological condition that may interfere with study assessments is excluded.
- 16. A Subject treated with hyperbaric oxygen therapy or a Cellular and/or Tissue Product (CTP) in the 30 days prior to the initial screening visit is excluded.

4.5 Study Schedule

The study is divided into two phases: Screening and Treatment Phases. The schedules for the protocol-specified assessments and procedures in each phase are detailed in the following sections. Note that there is an end of study visit (EOS1) scheduled on Week 13 or

Confidential Page 21 of 73

earlier if the wound heals or does not demonstrate at least 50% wound area reduction at 6 weeks after randomization (Week 7) and a follow-up visit (HCV1) to confirm that a wound is healed two weeks after first being assessed as healed.

4.5.1 Visit Windows

Subject visit dates must be scheduled within the visit windows detailed in the Schedule of Study Visits table. One week equals 7 days (± 3 days). During the Screening Phase, each visit is scheduled, with reference to the allowed visit window. During the Treatment Phase, each visit is also scheduled with reference to the allowed visit window.

Confidential Page 22 of 73

TABLE 1: SCHEDULE OF VISITS. LIGHT GREY (SCREENING); LIGHT YELLOW (TREATMENT); LIGHT BLUE (END OF TREATMENT VISIT); LIGHT PURPLE (ADDITIONAL WOUND HEALING CONFIRMATION VISIT FOR THOSE WOUNDS THAT HEAL)

			Wk 1 TV1		Wk 2	Wk 3	Wk 4	Wk 5	Wk 6	Wk 7	Wk 8	Wk 9	W 10	W 11	W 12	W 13*	
Visit	SV1	SV2	Pre Rand	Post Rand	TV2	TV3	TV4	TV5	TV6	TV7	TV8	TV9	TV10	TV11	TV12	EOS 1	HCV1
Weeks from Randomization Date	-2	-1	0		1	2	3	4	5	6	7	8	9	10	11	13	2 weeks after initial healing
Window Period	±3 days	±3 days	±3 da	ays**	±3 days	±3 days	±3days										
Assessment of eligibility	х	х	х														
Informed consent	Х																
Ulcer history	Х																
Demographics	Х																
Medical History or changes	х	Х	х		Х	Х	х	Х	Х	Х	х	Х	Х	х	Х	Х	х
Prohibited Therapies assessment	х	х	х		х	х	х	х	х	х	х	х	х	х	х	х	х
Medication assessment	х	х	х		х	х	х	х	х	х	х	х	х	х	х	х	х
ABI/SPP/TCOM/ TBI or arterial Doppler study	x																
Randomization				Х													
WOUND-Q instrument assessment	x					x				x						х	
Ulcer assessments	Х	Х	Х		Х	Х	Х	Х	Х	Х	Х	Х	Х	X	Х	Х	
Infection assessment of index ulcer	х	х	х		x	X	х	Х	X	Х	x	Х	х	X	Х	Х	
Physical exam or changes	х	х	х		х	Х	х	х	Х	х	х	Х	х	х	Х	Х	х
Vital signs	Х	Х	Х		Х	Х	Х	Х	Х	Х	Х	Х	Х	Х	Х	Х	Х
Assess for Adverse Effects and Adverse Events					x	x	x	x	x	x	x	х	x	x	х	х	Χ ^[A]

Confidential Page 23 of 73

			Wk 1	TV1	Wk 2	Wk 3	Wk 4	Wk 5	Wk 6	Wk 7	Wk 8	Wk 9	W 10	W 11	W 12	W 13*	
Visit	SV1	SV2	Pre Rand	Post Rand	TV2	TV3	TV4	TV5	TV6	TV7	TV8	TV9	TV10	TV11	TV12	EOS 1	HCV1
Urine or blood pregnancy test control (females of childbearing potential)	х								x								
Assurance of effective birth control (females of childbearing potential)	х								х								
Pain assessment	Х	Х	Х		Х	X	Х	Х	Х	Х	Х	Х	Х	Х	Х	X	Х
Monofilament Test with vibratory (10 point)	x	x	x		X	X	X	x	x	X	x	x	X	x	x	х	х
Serum Creatinine	Х																
Blood Sugar	Х	X	Х		Х	X	Х	Х	Х	Х	Х	Х	Х	Х	Х	Х	Х
HbA1c Lab	Х															Х	
Take X-ray to rule out osteomyelitis or bone infection	х																
SnapshotNIR	Х		Х		Х		Х			Х						Х	
Index ulcer photographs	х	х	Х		Х	Х	Х	Х	Х	Х	Х	Х	Х	Х	Х	х	х
Index ulcer measurements	х	х	Х		Х	X	Х	Х	Х	Х	Х	Х	Х	Х	Х	Х	X ^[A]
Assess index ulcer healing > 50%										X							
Index ulcer cleaning	X	х	х		X	X	х	х	х	х	х	х	х	X	х	Х	X ^[A]
Index ulcer debridement	X ^[B]	X ^[B]	X [B]		X ^[B]	X ^[B]	X ^[B]	X [B]	X ^[B]	X ^[B]	X [B]	X [B]	X ^{B]}	X [B]	X [B]	X ^[B]	X [A]
Index ulcer closure assessment			х		Х	X	х	х	х	х	х	х	х	X	х	Х	X _[c]
Assessment of offloading	х	х	х		х	X	Х	х	х	Х	Х	х	Х	Х	х	Х	x
Apply MIRRAGEN™ or FIBRACOL™				X	х	X	X	х	х	X	Х	х	X	X	х		
Apply outer dressing	Х	Х		X	X	X	X	X	X	X	X	Х	X	X	X	X ^[D]	X ^[D]

Confidential Page 24 of 73

[A]: Only assess for reopening of wound; [B]: If required per guidelines; [C]: Confirmation of wound closure; [D] Only if subject is not healed

Confidential Page 25 of 73

^{*}Will be earlier if wound heals before this date or subject is withdrawn from the study.

^{**}Visit windows applicable given that TV1 is at least 14 days from SV1. Subject MUST complete a minimum of a 14-day screening period.

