4.5.5 HCV: Healing Confirmation Visit

Perform the following procedures and assessments at this visit:

- Medial History Changes from previous visit
- Physical examination changes from previous visit
- Assess concomitant medications, changes from previous visit and prohibited therapies
- Vital signs
- Pain assessment (see section 8.9)
- Assess Blood glucose
- Assessment of offloading
- Index ulcer foot neuropathy Semmes Weinstein 10-point test with vibratory; See section 8.14
- Check for any changes in the subject's health and assess them for any adverse effects and adverse events
- If wound has re-opened, clean index ulcer
- If wound has re-opened, apply outer layer dressing
- Debridement of the index ulcer if applicable (see Appendix E)
- Digital imaging of the index ulcer
- If wound has re-opened, index ulcer measurements
- Confirm that the wound remained completely epithelized
- If wound has re-opened, document any other index ulcer assessments. If this is the EOS
 visit, discharge the subject from the study and make an appointment for the subject with
 their desired clinician for follow-up care; otherwise continue subject in study with allocated
 treatment schedule

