8.10 Ulcer Assessments

A number of different index ulcer assessments are required, including appearance, exudate characteristics, infection, and peri-wound characteristics.

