8.10.3 Index Ulcer Infection Assessments

The presence/absence of the following signs of infection at the index ulcer site will be documented at each visit. Infection of the index ulcer will be assessed using the STONEES method developed by Woo and Sibbald.¹⁹ Table 3 below lists the criteria for considering an index ulcer infected:

TABLE 3: INDEX ULCER INFECTION ASSESSMENT

Index Ulcer Infection Assessment Three or more of the following signs or symptoms are present: Increased surface area Increased peri-wound margin temperature by more than 3°F difference between two mirror image sites Exposed bone or can be probed to the bone

Confidential Page 46 of 73

- New areas of breakdown or satellite lesions
- Presence of swelling or reddened skin in peri-wound area
- Increased wound drainage
- Unpleasant, sweet, or sickening odor present

NOTE: An ulcer that Is deemed to be infected with three or more of the following signs will undergo a wound culture to confirm the presence of infection and identify the pathogenic organism, so the study subject receives the most appropriate antibiotic treatment

Infection at Index Ulcer site prior to Randomization

If the infection occurs prior to randomization i.e., prior to TV1, then the subject will be ineligible to be randomized.

Infection at Index Ulcer site after Randomization

If infection of the index ulcer site occurs after randomization *i.e.*, after the Randomization visit, record the infection as an adverse event and treat it as appropriate with oral antibiotics at the discretion of the Investigator.

Note: application of topical antibiotics and anti-microbial dressings to the index ulcer site are prohibited.

A subject with an infected index ulcer that is being treated by the Investigator will remain in the study unless the situation requires an alternative methodology that violates the protocol. Antibiotic interventions will be recorded on the Concomitant Medications CRF, and the event will be categorized as an Adverse Event, serious if it meets the definition of that category. All subjects who show evidence of an ulcer infection must have it reported on an Adverse Event CRF.

All subjects will be instructed to contact the Investigator if signs or symptoms of infection develop prior to their next scheduled visit.

During an episode of infection, the Investigator should not continue TCC, if it is being used, until the infection is resolved, and dressings should be changed at least every 72 hours.

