10.1 SOC Adverse Events

Since this a post market study involving commercially available SOC dressings of FDA cleared and approved medical devices; adverse events associated with their use may also require reporting to FDA.

An AE is defined as any unfavorable or unintended sign, symptom or disease that occurs or is reported by the subject to have occurred, or a worsening of a pre-existing condition related to the procedure or medical treatment (device/drug) used. All AEs related to the study procedure or medical treatment, including intercurrent illnesses, must be recorded in the subject's medical records and on the CRF. CTCAE v4.0 will be used for AE reporting.

AEs will be defined as those events that occur after the first study treatment is applied at TV1, through the final study visit. A description of the AE along with the onset date, end date, severity, action taken, treatment, outcome, likely cause and relationship to the study procedure or products will be recorded in the CRF.

AEs associated with each treatment arm will be tabulated and compared at the end of the study. AEs will be elicited through direct questioning, subject reports, and physical examination.

An abnormal laboratory test result is not by itself considered to be an AE unless the Investigator considers the finding of clinical significance that should be reported in such a manner.

The Investigator is responsible for assessing the relationship of the AE to the procedure or medical treatments used and the seriousness and expectedness of the AE at the time of occurrence. A medically qualified person appointed by the Sponsor will also assess this once the Sponsor has been notified of an AE. All AEs that occur during the trial will be documented on the AE CRF.

AEs reported during the study should be followed to resolution of the AE or within thirty days from the end of the study. A final assessment of the outcome will be made at that time.

Each AE related to the study procedure or medical treatment used will be categorized as "serious" or "not serious," based on the definition of a serious adverse event (SAE). An SAE is defined as an AE resulting in at least one of the outcomes described in Section 10.1.3.

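### Table 1 limits the adverse-event check at the Healing Confirmation Visit to wound reopening and schedules no infection check there, in conflict with Sections 4.5.5, 8.10.3 and 10.1

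*Combined protocol and SAP*

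**What the plan says.** Table 1 in Section 4.5.1 has a row "Assess for Adverse Effects and Adverse Events". It is marked plainly from TV2 to EOS1; only the HCV1 cell carries footnote [A], which reads "A]: Only assess for reopening of wound". The same footnote sits on index ulcer measurement, cleaning and debridement at HCV1. The row "Infection assessment of index ulcer" is marked from SV1 to EOS1 and is blank at HCV1.

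Section 4.5.5, the procedure list for HCV1, says without condition: "Check for any changes in the subject's health and assess them for any adverse effects and adverse events". It lists no standing infection check. It does say "If wound has re-opened, document any other index ulcer assessments", and Section 8.10 explains what such assessments cover: "A number of different index ulcer assessments are required, including appearance, exudate characteristics, infection, and peri-wound characteristics".

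Section 8.10.3 says: "The presence/absence of the following signs of infection at the index ulcer site will be documented at each visit". It also requires every ulcer infection to be entered on an adverse-event form. Section 10.1 sets the collection window: "AEs will be defined as those events that occur after the first study treatment is applied at TV1, through the final study visit". It adds that events will be tabulated and compared by arm.

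**The concern.** A site cannot follow both Table 1 and Section 4.5.5 at HCV1. One confines the adverse-event question to reopening; the other does not. The infection instruction conflicts in the same way with 8.10.3.

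The data at stake are comparative. Section 3 makes treatment-emergent adverse events a secondary endpoint and infection or cellulitis an exploratory one, and Section 9.2 has the interim analysis look at adverse effects such as infection. HCV1 exists only for subjects first judged healed, and no other visit is scheduled in the two weeks before it. The restriction thus depends on outcome, and the plan expects healing to be twice as frequent in one arm. Sites that resolve the conflict differently would also collect adverse events to different standards.

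**Working it through.** **1. The instructions for HCV1, side by side**

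| Item | Table 1 | Section 4.5.5 | Other text |
|---|---|---|---|
| Adverse events | Reopening only, [A] | Unrestricted | 10.1: collected to the final study visit |
| Infection signs | Blank | Only through other ulcer assessments, if reopened (8.10) | 8.10.3: every visit |
| Measurement, cleaning | [A] | Only if reopened | Agree |
| Debridement | [A] | If applicable, with no reopening condition | Disagree |

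For a subject whose healing is confirmed, HCV1 comes after EOS1 and is the last visit, so it lies inside the 10.1 window. Footnote [A] suits measurement and cleaning. It does not suit the adverse-event row.

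**2. The plan's planning figures**

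Inputs from Section 9.2: 120 per arm, healing 0.70 v 0.35, two-sided alpha 0.049, pooled Z-test, stated power 100%. The power is not in dispute; it is reproduced only because its healing rates are used below.

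- Pooled proportion: (0.70 + 0.35)/2 = 0.525.
- Standard error under the null: √(2 × 0.525 × 0.475/120) = 0.0645.
- Standard error under the alternative: √((0.70 × 0.30 + 0.35 × 0.65)/120) = 0.0604.
- Power: Φ((0.35 − 1.969 × 0.0645)/0.0604) = 0.9999, which agrees with the stated figure.

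**3. Visits on which the restriction falls**

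- MIRRAGEN: 120 × 0.70 = 84.
- FIBRACOL: 120 × 0.35 = 42.

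This takes one HCV1 per healer. Ulcers judged closed that then reopen would add visits in either arm.

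**4. Events that could be lost**

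The documents give no event rate, so both inputs here are assumptions: a share q of healers with an event other than reopening before HCV1 (2% to 10%), and a share m of those events missed (25% to 100%). Lost events = visits × q × m.

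- MIRRAGEN: from 84 × 0.02 × 0.25 = 0.42 to 84 × 0.10 × 1 = 8.4.
- FIBRACOL: from 42 × 0.02 × 0.25 = 0.21 to 42 × 0.10 × 1 = 4.2.

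**5. Ascertainment over the whole trial**

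Full adverse-event checks per subject, leaving out HCV1, are p × h + (1 − p) × (6f + 12(1 − f)). Here p is the healing rate, h the mean week of healing, and f the share of non-healers who exit at TV7. A TV7 exit has 6 checks (TV2 to TV7); a full course has 12 (TV2 to EOS1). Both h and f are assumed.

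| h | f | MIRRAGEN | FIBRACOL |
|---|---|---|---|
| 6.5 | 0 | 8.15 | 10.08 |
| 6.5 | 0.5 | 7.25 | 8.12 |
| 6.5 | 1 | 6.35 | 6.18 |
| 9 | 0.5 | 9.0 | 9.0 |

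For the first row: 0.70 × 6.5 + 0.30 × 12 = 8.15, and 0.35 × 6.5 + 0.65 × 12 = 10.08. The order of the arms changes with the assumptions.

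**The case against.** The best defence is that the full check is already required. Section 4.5.5 is the visit-specific list, and 10.1 says that events are elicited by questioning, subject report and examination, and that all of them are documented. This stands in part: harm arises only where a site follows the footnote instead. But the protocol states no order of precedence between Table 1 and the text, so that risk remains.

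Second, HCV1 is not otherwise empty. Table 1 marks history changes, medications, examination, vital signs, pain and photographs there without restriction. Unscheduled visits are allowed (4.5.6), subjects are told to report signs of infection (8.10.3), and serious events go to the CRO or sponsor within 24 hours of the site's awareness (10.1.3.1). This also stands, and it rules out saying that an event in those two weeks is caught at HCV1 or lost. Incidental detection is still not the same as a scheduled question.

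Third, several signs in 8.10.3 have little meaning on a closed, dry wound, and Table 1 leaves the whole ulcer-assessment row blank at HCV1, so the omission may be deliberate. If so, 8.10.3 should say so; as written, it makes no exception.

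A reader might infer that the restriction under-counts harms in the MIRRAGEN arm and so favours it. The documents do not support that as a finding. HCV1 is an extra visit that non-healers never have, so restricting it takes away nothing that non-healers receive. The TV7 exit shortens follow-up among non-healers, whom the plan expects to be more numerous under FIBRACOL, and step 5 shows that the balance can fall either way. Nor is the two-week interval unobserved: 168 v 84 subject-weeks (84 × 2 and 42 × 2) would be an exposure count, not a bias. The infection endpoint is set at 12 weeks, so an HCV1 that follows healing later than week 10 (10 + 2 = 12) falls outside it.

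**Conclusion.** The contradictions are real and can be read directly from the text. Table 1 conflicts with 4.5.5 and 10.1 on adverse events at HCV1. Table 1 and 4.5.5 both fall short of 8.10.3 on infection; what 4.5.5 lacks is an unconditional check, since a reopened wound is covered indirectly.

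Where sites follow Table 1, events other than reopening in the two weeks after healing may be missed or captured unevenly. If the planned healing rates hold, this touches about 84 MIRRAGEN and 42 FIBRACOL visits, a ratio of 2 to 1, and it can distort the adverse-event and infection comparisons. The number of events lost could be negligible or several per arm (0.4 to 8.4 v 0.2 to 4.2), on assumed rates only. The net direction across the trial is not established. The point concerns the quality of safety data; the primary endpoint is unaffected. It should be corrected as an internal inconsistency.

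**What to change.** Remove footnote [A] from the adverse-event row at HCV1, so that Table 1 agrees with 4.5.5 and 10.1. Mark the infection row at HCV1 and add the 8.10.3 check to the 4.5.5 list, so that both agree with 8.10.3. Keep [A] on measurement and cleaning, where it matches 4.5.5. Reconcile the [A] on debridement with the wording of 4.5.5; which of the two is intended is for the sponsor and clinicians to state.

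The cost is two table cells, one added line and the debridement reconciliation, at a visit that already takes place. No sample size, power or alpha figure changes.

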4.5.2 Screening Phase

The subject will sign and date the ICF and HIPAA authorization (according to site practices) prior to the collection of any protected health information, as well as any study-related procedures. A screening number will be assigned to each subject in successive order of entering the study after signing the ICF at each center, beginning with 001 at each site.

The screening phase may be broken into two visits. SV1 can occur up to 14 days prior to Randomization. SV2 should occur seven days prior to randomization.

SV1: Procedures to be performed include:

- Informed consent will be obtained prior to the collection of any protected health information as well as any study related procedures and the subject will sign a written ICF
- Assess current wound therapies for anything prohibited within 30 days of Randomization
- Demographics
- Medical history
- Physical examination
- Assess concomitant medications and any prohibited therapies
- Vital signs
- Pain assessment (see section 8.9)
- Labs: HbA1c (if no documented results within 90 Days of Randomization are available), assess blood glucose, and serum creatinine (if no documented results within 6 months of Randomization are available)
- Pregnancy test (blood or urine) if female subject is of childbearing potential. If female is not of childbearing potential the reason for inclusion must be included in the study record
- Assurance of effective birth control if female subject is of childbearing potential
- Ulcer history
- Index Ulcer assessment
- Assess signs and symptoms for clinical infection of the index ulcer (see section 8.10.3)
- Index ulcer foot neuropathy Semmes Weinstein 10-point test with vibratory; See section 8.14
- Clean the index ulcer
- Debridement of the index ulcer, if applicable (see Appendix E)
- Digital imaging of the index ulcer
- Record Index ulcer measurements
- Obtain X-ray to rule out osteomyelitis or bone infection of the affected foot
- ABI, SPP, TCOM, TBI, PVR measurement or Arterial Doppler Study will be obtained (see Appendices B-D)
- Initiate offloading of the index ulcer
- WOUND-Q

Confidential Page 26 of 73

- Assessment of subject's eligibility to continue in the study
- Apply appropriate SOC to index ulcer and outer dressing
- SnapshotNIR (at select sites)

SV2: Procedures to be performed include:

- Medical history changes from previous visit
- Physical examination changes from previous visit
- Assess concomitant medications, changes from previous visit and prohibited therapies
- Vital signs
- Pain assessment (see section 8.9)
- Assess blood glucose
- Index ulcer assessment
- Assess signs and symptoms for clinical infection of the index ulcer (see section 8.10.3)
- Index ulcer foot neuropathy Semmes Weinstein10 point test with vibratory; See section 8.14
- Clean the index ulcer
- Debridement of the index ulcer if applicable (see Appendix E)
- Digital imaging of the index ulcer
- Record Index ulcer measurements
- Assessment of offloading
- Assessment of subject's eligibility to continue in the study
- Apply appropriate SOC to index ulcer and outer dressing

A panel of three board-certified plastic surgeons will review each wound, as well as inclusion/exclusion criteria, in a blinded fashion to ensure that randomizations are appropriate. The review will occur between SV2 and the day of randomization. The plastic surgeon will provide correspondence to the trial manager that the subject is appropriate for randomization, prior to the site being able to randomize the patient.

